9.3.3 Exploratory Hypothesis

There are no hypotheses for the exploratory endpoints

9.4 Sample Size Determination

This study is a non-inferiority design, and sample size calculation was based on non-inferiority tests for SRT (Speech Recognition Threshold) scores and CNC word scores. The sample size using a confidence interval method (one-tailed 97.5% confidence interval) was estimated to have a reasonable power to detect non-inferiority of sentence and word scores for the above-mentioned hypotheses.

To reject the null hypothesis of inferior sentence in noise scores (SRT scores), the following parameters for sample size calculation were chosen:

- A clinical important difference value of 1 dB SRT. This margin is based on clinical consensus.
 NB: higher SRT scores represent poorer performance.
- A standard deviation (SD) of change or difference scores of 1.36 dB. This SD is calculated from 256 paired differences and is an indicative test re-test SD for both S0N3 and S0N0.
- A significance level $\alpha = 0.025$ (one-tailed).
- A desired power of 0.8

Based on these assumptions, a sample size of 17 are required to reject the null hypotheses. Twenty subjects will be enrolled to allow for any unforeseen subject withdrawal.

9.5 Analysis Populations

The analysis of the primary endpoint will be based on the Intent-To-Treat (ITT) and Per Protocol (PP) analysis populations in order to support a conclusion of non-inferiority. The inclusion of both ITT and PP populations has been chosen to assess the robustness of the study results and the consistency of the study measures under different analysis populations.

Clinical Investigation Plan: CLTD5804

This study has a non-inferiority design; therefore, the primary analysis will be based on the PP population.

For cases in which the ITT and PP populations lead to the same conclusions and final interpretations about the treatment effect, the results will be considered to not be influenced by underlying factors such as missing data and protocol deviations, and the results would be considered to be robust and consistent under different analysis populations. A statement to reflect this will be included in the CIR.

For cases in which the ITT and PP populations lead to different final interpretations or conclusions, all of the results will be reported and the differences in outcomes will be identified and explored.

Intent-to-Treat Population

The Intent-to-Treat Population will include all subjects who receive the treatments and have at least one set of paired treatment and control measurements from any endpoint, regardless of protocol deviations and missing data.

Per Protocol Population

The Per Protocol Population will include all subjects who receive the treatments and have at least one paired measurement from treatment and control, without major protocol deviations. Major deviations will be defined at the clean file meeting before data base lock.

It is possible that a treatment has not been administered in the intended counterbalanced order of presentation. It is also expected that the sequence and period effects are minimal in this study if any. This study is not a full cross-over design, so period and sequence effects will not be assessed, without the consequence to bias the study conclusion.

Safety Population

The Safety Population will include all treated subjects. The Safety Population will be used for the safety data analysis.

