7.2.6 Criteria for Subject Withdrawal

Subjects can decide to withdraw from the investigation at any time. The Investigator shall ask the reason(s), however, subjects have the right to withhold their reason if preferred. The reason for withdrawal should be documented in the subject's source files and the case report form (CRF).

The Investigator or Sponsor may also decide to withdraw a subject from the clinical investigation if it is considered to be in the subject's best interests.

Subject withdrawal may be for any of the following reasons:

- Adverse Event (AE)
- Device Deficiency (DD)
- CIP or GCP deviation
- Subject withdrew consent
- Subject lost to follow-up
- Subject death
- Sponsor decision
- Investigator decision

If a subject is lost to follow-up, every possible effort must be made by the study site personnel to contact the subject and determine the reason for discontinuation. At least 3 separate attempts taken to contact the subject must be documented.

Participating subjects who are withdrawn/discontinued will not be replaced.

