11.5 Independent Data Monitoring Committee

The risks associated with the use of the investigational device and the subject's participation in the clinical investigation is described in Section 8.3 of this document. The subjects in the proposed clinical investigation will be able to revert to their own processor if there are sound quality issues or dissatisfaction with the investigational sound processors. As this study is an open label study, no Independent Data Monitoring Committee (IDMC) has been established for this clinical investigation.

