4.4 Additional Statistical Considerations

4.4.1 Missing, Unused or Spurious Data

See Section 4.3 for the intended treatment of missing or spurious data, such as CIP deviations.

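### Agreement between ITT and PP cannot show that missing S0N90 pairs left the primary result uninfluenced, yet CIP 9.5 has the report say so

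*Protocol*

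**What the plan says.** CIP 9.5 makes PP the primary analysis population, with ITT alongside it to assess robustness. If the two lead to the same conclusion, "the results will be considered to not be influenced by underlying factors such as missing data and protocol deviations", and a statement to that effect goes into the investigation report.

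The sets are defined as follows.

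- **ITT:** subjects who received the treatments and "have at least one set of paired treatment and control measurements from any endpoint", "regardless of protocol deviations and missing data".
- **PP:** subjects with "at least one paired measurement from treatment and control, without major protocol deviations". The endpoint is not named. Major deviations are settled at the clean file meeting.

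The main analysis of the primary endpoint is the 95% CI of the mean paired S0N90 difference, compared with 1 dB (CIP 9.6, SAP 4.5). On missing data, SAP 4.4.1 says only: "See Section 4.3 for the intended treatment of missing or spurious data, such as CIP deviations". SAP 4.3 contains the population definitions and no rule for a missing value. The SAP does not repeat the robustness sentence of CIP 9.5.

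Words in quiet are tested at Visit 1 and both noise conditions at Visit 2 (CIP 3 and 7.3). CIP 7.2.6 lists adverse event and device deficiency among the withdrawal reasons and adds: "Participating subjects who are withdrawn/discontinued will not be replaced".

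**The concern.** A comparison of two analyses can reveal the influence of a factor only if the analyses treat that factor differently. Here both leave out the same subjects with no S0N90 pair. A subject who leaves after Visit 1, or who stops at Visit 2 before both processors have been tested in S0N90, may belong to the ITT set through a words-in-quiet pair. That subject still has no primary difference to contribute.

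The direction matters in a non-inferiority trial. If the missing subjects would have done worse on Nucleus 8, leaving them out moves the estimate towards non-inferiority. ITT and PP would move together, and the report would then carry a statement about missing data that the comparison cannot support.

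**Working it through.** **1. The plan's own figure.** CIP 9.4 and SAP 4.1 give margin 1 dB, SD of paired differences 1.36 dB, one-sided alpha 0.025, power 0.8, 17 subjects required and 20 enrolled. The true difference is not stated. Assuming 0 dB, a paired non-inferiority t-test (noncentral t) has power 0.785 at n = 16 and 0.812 at n = 17. The figure of 17 reproduces, and the allowance for loss is 20 − 17 = 3.

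**2. Who contributes to the primary estimate.**

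| Subject has | In ITT set | In PP set | In ITT estimate | In PP estimate |
|---|---|---|---|---|
| S0N90 pair, no major deviation | yes | yes | yes | yes |
| S0N90 pair, major deviation | yes | no | yes | no |
| Pair on another endpoint only, no major deviation | yes | yes | no | no |
| Pair on another endpoint only, major deviation | yes | no | no | no |
| No pair at all | no | no | no | no |

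The two estimates differ only through the second row. If that row is empty, they use the same data and must agree, whatever the reason for the missing pairs.

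**3. Observed result with 17 pairs.** Assume observed mean 0 and SD 1.36 dB.

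Upper limit = 0 + t(0.975; 16 df) × 1.36/√17 = 2.120 × 0.3298 = 0.70 dB. This is below 1 dB, so non-inferiority is declared.

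**4. Tipping value.** Let k subjects be missing, 20 − k observed with mean d and SD 1.36, and give each missing subject the difference M.

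- mean = [(20 − k)d + kM]/20
- SS = (19 − k) × 1.36² + (20 − k)(d − mean)² + k(M − mean)²
- upper limit = mean + t(0.975; 19 df) × √(SS/19)/√20

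For k = 3, d = 0 and M = 2.1:

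- mean = 6.3/20 = 0.315
- SS = 29.59 + 1.69 + 9.56 = 40.84
- SD = √(40.84/19) = 1.466
- upper limit = 0.315 + 2.093 × 1.466/4.472 = 0.315 + 0.686 = 1.00 dB

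Solving for M at an upper limit of 1 dB:

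| Observed mean (dB) | Missing subjects | Tipping value M (dB) |
|---|---|---|
| 0 | 3 | +2.1 |
| 0 | 2 | +2.8 |
| 0 | 1 | +4.5 |
| +0.2 | 3 | +1.4 |
| −1.07 | 3 | +4.9 |

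The last row borrows, as an assumption, the size of the 1.07 dB improvement that CIP Table 2 cites from CLTD5709.

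**5. Upper illustration of the error rate.** Trials of 20 differences were simulated from a normal distribution with mean 1 dB (the margin) and SD 1.36 dB, and the complete-pair interval was applied. With no loss or random loss, non-inferiority is wrongly declared in about 2.5% of trials. If the worst 1, 2 or 3 of the 20 have no pair, the rate is about 7 to 8%, 15% or 26%. With no major deviations, ITT and PP agree in every run. With one or two subjects removed from PP at random, they still agree in 93 to 97% of these worst-loss runs.

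**The case against.** Much can be said for the plan.

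- **Partial missingness.** Each condition has two or three lists, and CIP 13 treats omitted or incomplete assessments as deviations to be documented. A subject with an incomplete set of S0N90 lists could stay in ITT and be removed from PP. The comparison then says something about incomplete testing classed as a major deviation. This stands. It does not reach a subject with no S0N90 pair.
- **Set membership.** A reader might infer that both populations exclude everyone without an S0N90 pair. They do not: ITT accepts a pair from any endpoint and PP names none. Such subjects fall out of the primary calculation, not out of the set.
- **Visibility.** A reader might infer that loss caused by Nucleus 8 would go undetected. The documents do not support that. Withdrawal reasons go into the CRF (CIP 7.2.6), AE-related discontinuations and device deficiencies are summarised (CIP 9.9), and the number contributing values is reported (SAP 4.5). What cannot be seen is the effect on the estimate.
- **Expected loss.** A reader might infer that the plan expects Nucleus 8 to drive subjects out, because CIP 11.5 says they may "revert to their own processor if there are sound quality issues or dissatisfaction with the investigational sound processors". That sentence belongs to the reasons for having no data monitoring committee, and all subjects return to their own processor after each session anyway. CIP 9.4 describes the allowance as being for unforeseen withdrawal. Product issues that affect performance lead to an update and re-testing (CIP 7.3), so many would not end in loss.
- **Selection.** The simulated rates assume loss chosen on the S0N90 difference itself. The test adapts to each subject's 50% point, both processors are compared in one session, and the BEAM program is first tested at Visit 2. The SD is described as an indicative test-retest value, so some of the worst differences are noise. Selection this strong is an extreme case.
- **The ANOVA.** SAP 4.5 does not say whether the subject term is fixed or random. A lone SRT adds nothing to the processor effect if it is fixed, but may add a little if it is random. The model is for comparison only and is not offered as a missing-data analysis.

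None of this restores the inference for wholly missing pairs.

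**Conclusion.** The concern holds for the missing-data part of the CIP 9.5 rule. ITT/PP agreement can speak to protocol deviations, including incomplete testing classed as a major deviation. It cannot speak to subjects with no S0N90 pair, and neither document has another analysis that does. This follows from the definitions and the paired estimator and depends on no assumed number.

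The practical size depends on how many pairs are missing and on the observed mean. Under SD 1.36 dB and the full allowance of three losses, the missing subjects would need to average about +2.1 dB to overturn an observed mean of 0. The value is about +1.4 dB at an observed mean of +0.2 and about +4.9 dB at −1.07. If Nucleus 8 performs as the sponsor predicts, the result would be hard to tip. The rates of 7 to 8%, 15% and 26% are an extreme upper illustration, not a forecast; random loss leaves 2.5%. With short testing at two visits, there may be few missing pairs or none.

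**What to change.** 1. **CIP 9.5:** remove missing data from the inference drawn from ITT/PP agreement, and limit the statement in the investigation report to protocol deviations.
2. **SAP 4.4.1:** commit to reporting how many subjects began testing but have no S0N90 pair, by reason and by the processor in use when testing stopped.
3. **SAP 4.4.1, only if pairs are missing:** give a simple supportive tipping value, namely the mean Nucleus 8 minus Nucleus 7 difference in those subjects at which the upper limit for all who began testing reaches 1 dB. Make no claim of robustness to missing data without it.

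The cost is a wording change in both documents and one small table, with no extra visits or tests. Withdrawal reasons and device deficiencies are already collected; the processor in use when testing stopped should be noted with them. The downside is that the robustness statement may be less favourable.

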9.6 Primary Endpoint Analyses

Primary and Secondary Speech Perception Endpoints:

SRT sentence scores in noise and words in quiet scores at different speech testing conditions will be listed and summarised descriptively by treatment group and study population. A Scatter plot or similar plot will be used to present the individual data by treatment group, and bar chart will be used to present the average paired difference and its standard error.

For the non-inferiority test of SRT sentence scores the 95% CI (alpha=0.025 one-sided) for the mean paired difference will be estimated. If the upper limit of the 95% CI of the mean paired difference is lower than 1dB, the treatment condition is regarded as non-inferior to the control in term of SRT sentence perception. The non-inferiority margin of 1dB for SRT is based on clinical consensus.

The same analysis method will be applied to the non-inferiority test for words in quiet scores (monosyllables). For the non-inferiority test of words in quiet scores, the 95% CI (alpha=0.025 one-sided) for the mean paired difference will be estimated. If the lower limit of the 95% CI of the mean paired difference is above -10%, the treatment condition is regarded as non-inferior to the control in

Clinical Investigation Plan: CLTD5804

term of words in quiet perception. The non-inferiority margin of -10% for words in quiet scores (monosyllables) is also based on clinical consensus.

Only when the non-inferiority test for the above specified endpoint is successful, then a superiority test for the endpoint will be further conducted to assess the treatment effect.

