4.3.2 Per Protocol Population

The Per Protocol analysis population will include all subjects who receive the treatments and have at least one paired measurements from treatment and control, without major protocol deviations. Major deviations will be defined at the clean file meeting before data base lock. The Per Protocol analysis population will be the main analysis population for non-inferiority test.

It is possible that a treatment has not been administered in the intended counterbalanced order of presentation. It is also expected that the sequence and period effects are minimal in this study if any. This study is not a full cross-over design, so period and sequence effects will not be assessed in the main analysis, without the consequence to bias the study conclusion. The paired difference between Nucleus 8 Sound Processor and Nucleus 7 Sound Processor will also be estimated after accounting for period and sequence effects.

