A paired t-test will be used to compare the above sound processor effect. While estimation of 95% CI of the paired difference is the main analysis method, an Analysis of Variance (ANOVA) approach will also be used to estimate the 95% CI of the paired difference, accounting for the cross-over design. The ANOVA model will account for the sequence and period effects when the sound processor effect is compared. The model takes the form:

$$\text{SRT} = \text{test} + \text{sequence} + \text{subject (nested in sequence)} + \text{period}$$

Sound processor effect estimated by the ANOVA model will be provided for comparison purpose, along with the results directly estimated by the paired data.

All demographics and baseline characteristics will be summarised descriptively. Any adverse events or device deficiencies will be listed in by-subject listings.

This study is for product development. For each pre-planned comparison, a 95% CI of the comparison difference will be estimated, with type I error controlled at the significance level of 0.05 (two-sided) for each endpoint.

For regulatory purpose, a pre-specified hierarchy test will be used to control type I error in strong sense. For non-inferiority test, significance test for each endpoint will be assessed at the significance level of 0.05 (two-sided), in the pre-specified order from the primary endpoint to the secondary endpoint 4. Only if the first endpoint is significant, then the test can be carried out to the next

endpoint. Continue until the test for one endpoint in the sequence is not significant and stop further testing. All the following tests are regarded as exploratory and will not be used for decision-making.

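### The non-inferiority decision ignores test order, and the assurance that this cannot bias the result holds only with no period effect or exactly equal orders

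*Protocol*

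**What the plan says.** CIP 7.2.7 counterbalances the test order and aims for even use of all permutations, but only as far as feasible. CIP 7.2.6 says that withdrawn participants are not replaced. CIP 9.5 and SAP 4.3.2 both concede that the plan may not be followed: "It is possible that a treatment has not been administered in the intended counterbalanced order of presentation". Both expect period and sequence effects to be small and give no figure.

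The two documents then differ. CIP 9.5 says that "period and sequence effects will not be assessed, without the consequence to bias the study conclusion". SAP 4.3.2 keeps the no-bias assurance but limits the omission to the main analysis, and adds an estimate that accounts for period and sequence. SAP 4.5 writes that model for SRT (test, sequence, subject within sequence, period) and gives it a supporting role: "Sound processor effect estimated by the ANOVA model will be provided for comparison purpose, along with the results directly estimated by the paired data". SAP 4.3.2 also says that the study is not a full cross-over, while SAP 4.5 justifies the ANOVA by the cross-over design.

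The decision itself is unadjusted. In CIP 9.6, "the 95% CI (alpha=0.025 one-sided) for the mean paired difference will be estimated", and its upper limit is compared with 1 dB, mainly in the Per Protocol population. SAP 4.5 calls the interval for the paired difference the main method. Neither document says which result governs if the interval and the ANOVA disagree.

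**The concern.** The two sentence-in-noise conditions are compared within one visit, so practice or fatigue could shift the second result relative to the first. The CIP itself names tiredness, motivation and attention as confounders (4.3), allows test periods of up to three hours (5.2), and gives the practice run only with the first combination to be tested (7.3).

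If such a shift exists, an unadjusted paired analysis suffers in two ways. With equal orders the shift stays in the error term and widens the interval. With unequal orders part of it moves into the estimated device difference, for or against Nucleus 8. Unequal orders are possible: withdrawals are not replaced, the order may be given wrongly, and Per Protocol exclusions are defined only at the clean file meeting. At stake are lost power in one direction, and in the other a non-inferiority claim made at more than the nominal 2.5%. With two reported estimates and no governing rule, there is also room to choose between them after seeing the data.

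**Working it through.** **Inputs.** From CIP 9.4: "A clinical important difference value of 1 dB SRT"; "A standard deviation (SD) of change or difference scores of 1.36 dB"; "A desired power of 0.8"; one-sided α = 0.025; 20 enrolled. Assumed, because the documents do not state them: a true device difference of 0 for power; π, the period 2 minus period 1 shift in SRT, from 0 to 0.5 dB; 1.36 dB as the SD within each order; each condition tested as one block.

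**1. The plan's own figure.** For a paired non-inferiority t-test, power comes from the noncentral t with n − 1 degrees of freedom and noncentrality √n × 1/1.36.
- n = 16: noncentrality 2.941, power 0.785.
- n = 17: noncentrality 3.032, power 0.812.

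This reproduces "a sample size of 17 are required to reject the null hypotheses". At n = 20 the noncentrality is 3.288 and power 0.877 (0.876 by simulation).

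**2. Unadjusted analysis.** Write each paired difference as d = τ + πs + e, with s = +1 if Nucleus 8 is tested second and −1 if first.
- Bias of the mean: π(n1 − n2)/n. At 12/8 and π = 0.5: 0.5 × 4/20 = 0.10 dB.
- SD of the differences: √(1.36² + π²[1 − ((n1 − n2)/n)²] × n/(n − 1)). At 10/10 and π = 0.5: √(1.8496 + 0.25 × 20/19) = 1.454 dB.

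**3. Adjusted analysis.** The estimate is the average of the two order-specific means, with SE = (1.36/2)√(1/n1 + 1/n2) and n − 2 degrees of freedom. Its power does not depend on π.
- 10/10: SE = 0.68 × √0.2 = 0.304, power 0.875.
- 12/8: SE = 0.310, power 0.861.
- 9/8: SE = 0.330, power 0.807.

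**4. Comparison.** Unadjusted values are simulated (100,000 or more runs, good to about 0.002). Where two values are given, the first is for an imbalance working against Nucleus 8 and the second for one favouring it.

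| Orders | π (dB) | Bias (± dB) | Power, unadjusted | Power, adjusted | Type I error, unadjusted |
|---|---|---|---|---|---|
| 10/10 | 0 | 0 | 0.876 | 0.875 | 2.5% |
| 10/10 | 0.25 | 0 | 0.868 | 0.875 | 2.3% |
| 10/10 | 0.5 | 0 | 0.845 | 0.875 | 1.9% |
| 9/8 | 0.5 | 0.029 | 0.745 / 0.797 | 0.807 | 1.5% / 2.3% |
| 12/8 | 0.25 | 0.05 | 0.833 / 0.899 | 0.861 | 1.6% / 3.3% |
| 12/8 | 0.5 | 0.10 | 0.763 / 0.907 | 0.861 | 0.9% / 3.9% |

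Adjusted type I error is 2.5% in every row.

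**5. Price of adjusting when π = 0.** The unadjusted analysis is then unbiased at any split.
- n = 20, unadjusted 0.877: adjusted 0.875 at 10/10 (0.2 points) and 0.861 at 12/8 (about 1.5 points).
- n = 17, unadjusted 0.812: adjusted 0.796 at 10/7 (about 1.5 points) and 0.773 at 6/11 (about 4 points).

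**6. Words in quiet.** CIP Table 3 has five conditions, so 5! = 120 orders; 20 participants cannot represent them evenly. The ANOVA in SAP 4.5 has SRT as its only response, so no adjusted model exists for the word scores.

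**The case against.** The documents expect order effects to be minimal, and two design features support that: a practice run precedes the scored sentence tests, and each comparison stays within one session. If the 2 or 3 lists per condition were interleaved, which the documents do not specify, any period effect would shrink further. At 11/9 and 0.25 dB the bias is only 0.025 dB and type I error at most about 2.8%. If there is no period effect, the unadjusted interval is valid at any split and slightly more powerful; at 10/7 or 6/11 adjustment would take power below the planned 0.80. The SAP already pre-specifies and reports the adjusted model, so an order effect would be visible.

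Most of this stands as a limit on size. It does not rescue the no-bias assurance, which is stated without its condition, and it does not settle which result governs.

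A reader might go further and infer that the planned analysis wastes power and is biased as it stands, or that unequal orders alone cause bias. The documents do not support that: both harms need a non-zero period effect, and no figure is given. A reader might also infer that type I error would double to about 5%. That needs 6/11 with a 0.5 dB effect favouring Nucleus 8 (4.9%). From 10/10, losing three participants gives at worst 10/7, where the error is between 3.3% and 3.4% at 0.5 dB; reaching 6/11 also needs someone tested in the wrong order.

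**Conclusion.** The point holds in conditional form. The non-inferiority decision leaves out test order although equal orders are not assured. The statement that this cannot bias the conclusion is correct only if π = 0 or n1 = n2. The CIP and SAP also disagree on whether order is assessed at all.

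The size depends on a period effect that the documents do not quantify. If it is minimal and the orders stay near balance, the loss is under one point of power and the bias about 0.03 dB or less against a 1 dB margin. At an assumed 0.5 dB the plan loses about 3 points of power at 10/10, can fall below the planned 0.80 at 9/8, and at 12/8 moves away from the nominal error rate in a direction that cannot be known in advance. The adjusted model holds 2.5% in all these cases. This is a worthwhile, inexpensive improvement, not a finding that the primary analysis is invalid. The figures cover the two-condition SRT comparisons only.

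**What to change.** - In SAP 4.5, make the SRT model already specified (test, sequence, subject within sequence, period), using the order actually given, the decision analysis for the primary endpoint and secondary endpoint 4, for both non-inferiority and superiority. Keep the paired t interval as a sensitivity analysis.
- Report the achieved order counts in each analysis population.
- Delete the no-bias wording in CIP 9.5 and SAP 4.3.2, and align the two documents on whether order is assessed and whether the design is treated as a cross-over.
- For words in quiet, a period-adjusted analysis would be new. If wanted, specify it as supportive; it is not a swap of two planned analyses.

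For SRT the cost is a wording change and one residual degree of freedom. The statistical downside, if there is no period effect, is about 0.2 points of power at 10/10, 1.5 points at 12/8 or 10/7, and 4 points at 6/11.
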